3. STUDY DESIGN

A partially-blinded, prospective, multi-centre, block-randomised controlled trial (RCT) is designed. After obtaining written informed consent, patients are registered centrally, FNAC is reviewed centrally and thereafter patients are randomised to either the experimental study-arm (arm A: FDG-PET/CT driven management decisions) or a control study-arm (arm B: surgery regardless FDG-PET/CT result) using a 2:1 allocation ratio. The latter is performed both for methodological purposes (the treatment of the subjects in the control study arm is well investigated and described before) and to satisfy the assumption that patient prefer the experimental study-arm. The result of randomization is blinded to the treating physicians and central FDG-PET/CT review committee. Allocation is adaptively stratified using the minimisation method on the centre of inclusion and the most prognostic features of DTC known at this stage of patient work-up: (US) lesion size (0-10 mm/11-20 mm/21-40 mm/40+ mm), patient sex, patient age (<45yr, \geq 45yr) and Bethesda classification according to central review committee (atypia of unknown significance/follicular lesion of unknown significance (III) or (suspicion) for a follicular neoplasia (IV)).

Based on the study arm allocation and PET result, treating physicians will either be told to cancel scheduled diagnostic thyroid surgery (allocation to the experimental arm with a negative FDG-PET/CT at central review or ~32/132 patients) or to proceed with surgery (all other cases or 100/132 patients). In case surgery is cancelled the patients need to be followed-up by watchful waiting and a confirmatory ultrasonography (including FNAC) after 12 months. Patient allocation will not be disclosed to prevent study withdrawal, however in case surgery is cancelled unblinding is unavoidable (~25% of all included patients).

The Gold Standard is histology, revised by a (central) dedicated pathologist panel, obtained from surgery or 12-months follow-up, including US (+FNAC). All patients will be followed for at least 12 months after FDG-PET/CT to ensure all direct costs and complications are noted. Five years after inclusion of the last patient, long-term follow-up will be determined based on patient file review and contact with the general practitioner (flowchart Figure 1, p34 and

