8.2.2 Randomisation, stratification, blinding and treatment allocation

The prognosis of thyroid carcinoma is mainly determined by Metastasis, patient Age, Completeness of resection, local Invasion, and tumour Size (MACIS [52]). Apart from these properties, sensitivity of FDG-PET/CT is mainly determined by nodule size and specificity is mainly deteriorated by follicular origin of the nodule. Only age, nodule size (on ultrasonography), cytological subtype and sex are known at the time of inclusion (Table 4, p48). Recently it was described that lesions larger than 40 mm (T3) carry a higher risk of malignancy compared to smaller lesions (odds ratio: 2.10, 95%-CI: 1.26-3.50) and that men have a higher risk of malignancy than women (odds ratio: 1.51, 95%-CI: 1.20-1.83) [53]. We will use a minimisation strategy [54] to stratify for centre (site) of inclusion, US size, Bethesda subtype, Age and Sex only, meaning that in case patients are homogenously

distributed between both treatment arms over all these four factors, 2:1 randomisation will take place, in all other cases, patients will be allocated to the arm in which this type of patient is underrepresented.

Patients will be randomised in a 2:1 fashion to the experimental and control study arm. Patients, treating physicians, central pathologists and nuclear medicine physicians will be blinded for allocation, however in case of an FDG-PET/CT negative nodule in the experimental study arm, patient and treating physician are unblinded as surgery needs to be cancelled. In all other cases, patients proceed to surgery, but patients and treating physicians are kept blinded with respect allocation of the patient (either FDG-PET/CT positive nodule in the experimental study arm or inclusion in the control study arm regardless of PET-result).

EfFECTS

Factor:	Level 1:	Level 2:	Level 3:	Level 4:
Ultrasonographic	T1a (0-10mm)	T1b (11-20mm)	T2(21-40mm)	≥T3 (>40mm)
Nodule Size:	(13%)	(37%)	(37%)	(13%)
Bethesda Subtype	III (AUS/FLUS)	IV (SFN)		
	(67%)	(33%)		
Age	<45yr (40%)	≥45 yr (60%)		
Sex	Female (80%)	Male (20%)		

 Table 4: Stratification during study including expected fractions (based on [4] and [51]).
 AUS/FLUS: Atypia

 of Undetermined Significance or Follicular Lesion of Undetermined Significance; Rep: repeatedly; SFN: (Suspicious for) Follicular Neoplasm.

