At the department of nuclear medicine, patients are prehydrated using 500 mL of tap water orally. An i.v. cannula is placed in a peripheral vein and about 3.45 MBq/ kg (<25% bed overlap) or 1.725 MBq/ kg (50% bed overlap) FDG (based on 3D acquisition, 4 min/bedpost) is injected intravenously after which the cannula can be removed. This administered FDG-dose may be adapted to local standards as long as these do not violate the current EANM guidelines [50, 55]. Adaptation to this those can be performed incorporating factors such as scanner sensitivity, scan speed and bed overlap.

The patient is incubated alone in a supine position for 60 minutes (+/- 5 minutes) in a warmed (thermoneutral) environment and asked to refrain from muscle activity (no talking, etc.). In case of severe claustrophobia, the use of a benzodiazepine (e.g. oxazepam 10 mg) is allowed.

After incubation, the patient is positioned in the scanner using a head rest to prevent motion mismatch between PET and CT. After a scout view (Figure 4, p50) and a low-dose, non-contrast enhanced CT, PET-acquisition of the head and neck is performed for at least 2 min per bed position. Two bed positions are usually enough to cover the range from the meatus acusticus externus to the fossa jugularis sternalis (or down to the lower margin of the arcus aortae in case of retrosternal goitre).

After the PET-acquisition, the scan is complete and the patient can go home without any further restrictions. The total examination takes around 1.5 hours. Images will be reconstructed using the departments own protocol, including corrections for isotope decay, attenuation, scatter,

dead time and are cross-calibrated to the dose-calibrator of the FDG-dose and in conjunction with the EANM guidelines [50, 55]. The reconstructed FDG-PET/CT images must not be reported and are digitally pseudonymised and submitted for central reading. The results of this examination will be withheld from the patients and treating physicians. Patients are eligible for compensation of the travelling expenses.

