8.3.4 Cytology and histopathology analysis

In the study, cytopathology and histopathology specimens are collected. After cytopathology is collected from individual patients during FNA (prior to study inclusion), cytopathology slides are reviewed at the Radboudumc by two experienced thyroid pathologists to ensure appropriate inclusion in the study. If the first and second pathologist disagree, a third dedicated pathologist will be consulted. Consensus upon classification as either Bethesda category III or IV has to be reached before inclusion of a patient into the study (§8.2.1, p46). Cytopathology samples are returned and stored in local tissue banks at the centre where the FNA was initially performed. Before start of the study, a consensus meeting was held with the dedicated pathologists from the different centres to minimise interobserver variation.

After surgery, thyroidectomy specimens are being stored at the hospital where the surgery has been performed and will be collected at the end of the study. After surgery in all appropriate study patients is completed, histopathology specimens will be reviewed at the Radboudumc by the same experienced thyroid pathologists but an expert of the LUMC may be consulted for specific cases. Characteristics of the lesion like type of lesion, size, cell type, inflammation and vascularity will be scored (see §8.1.2, p45) in adherence to the World Health Organization guidelines [64].

Next, cytological and histopathological tissue characteristics will be analysed in relation to FDG-PET/CT findings in order to determine whether specific tissue characteristics can explain false positive or negative FDG-PET/CT results - like for instance high vascularity or cell type.

Definition of malignant and benign thyroid nodules:

A nodule is considered malignant, in case malignancy is diagnosed at the location of the nodule. All other cases are considered benign nodules.

[figure not shown]
Following advanced insights and in accordance with WHO guidelines, pre-malignant entities such as non-invasive follicular thyroid neoplasm with papillary-like nuclear features (NIFTP), follicular tumor of uncertain malignant potential (FT-UMP) and well-differentiated tumor of uncertain malignant potential (WDT-UMP) are distinguished. These are strictly considered benign though potentially precancerous lesions, for which thyroid lobectomy is justified [65, 66].

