As such, a FDG-PET/CT scan is considered true positive if the nodule that was FDG-avid harbors any type of histopathology that warrants surgery, including malignancy, NIFTP, FT-UMP and WDT-UMP. If such a nodule is non-FDG-avid, it will be considered false-negative.

In case a DTC microcarcinoma (T1a or diameter ≤10mm) is found within a much larger nodule, this is considered a coincidental finding. The patient will be treated for DTC (in the special case of a papillary unifocal microcarcinoma, according to the guidelines one can suffice with a therapeutic hemithyroidectomy without completing thyroidectomy and ¹³¹I-RIA [5]). In case this much larger nodule was positive on the FDG-PET/CT, it is considered false-positive; in case the nodule was negative on the FDG-PET/CT, it is considered true-negative.

Lesion-by-lesion qualification of thyroid nodules:

Five locations are considered (left/right lobe with upper/lower pole and central: isthmus/lobus pyramidalis: Figure 6, p54). Qualification of the PET result to be true or false is based on anatomically matched locations (e.g. an FDG-PET/CT positive lesion at the location of a malignant nodule is a true-positive result). In case in doubt (e.g. a node centrally in the left or right lobe), consensus reading by pathologist, surgeon and nuclear medicine physician Figure 6: Anatomy and subdivision of the will be performed.

normal thyroid gland

Multifocality:

In case the patient receives surgery for a FDG-negative nodule (only in the control arm) but this nodule is found to contain malignant tissue, the patient is considered false-negative.

If, however, in the same patient a second malignant nodule is found in the contralateral thyroid lobe at completion thyroidectomy, which was positive on PET ("true-positive"), the patient is considered false-negative and thus the treatment following the PET-scan unbeneficial.

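### Section 8.3.4 does not keep the location part of the reference label independent of the PET result, so the accuracy estimates and the control-arm false-negative count are open to review bias

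*Protocol*

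**What the plan says.** Section 3 sets the reference: "The Gold Standard is histology, revised by a (central) dedicated pathologist panel, obtained from surgery or 12-months follow-up". Section 8.3.4 says that "histopathology specimens will be reviewed at the Radboudumc by the same experienced thyroid pathologists", once surgery in all relevant patients is complete.

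The label depends on place as well as tissue: "A nodule is considered malignant, in case malignancy is diagnosed at the location of the nodule"; every other case is benign. For the PET verdict, 8.3.4 states: "Qualification of the PET result to be true or false is based on anatomically matched locations". Five locations are used: upper and lower pole on each side, and a central isthmus/pyramidal region. Where the location is unclear, for example a nodule in the middle of a lobe, the matter is settled by "consensus reading by pathologist, surgeon and nuclear medicine physician".

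On blinding, 8.2.2 says: "Patients, treating physicians, central pathologists and nuclear medicine physicians will be blinded for allocation". Section 8.3.1 says of the scan: "The results of this examination will be withheld from the patients and treating physicians".

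**The concern.** Location enters the definition of malignancy, so deciding that a cancer lies in the index nodule or beside it can move a patient between the true-positive, false-positive, false-negative and true-negative cells. It can also turn an operation from beneficial to unbeneficial. The five-region map has no mid-lobe position, and a nodule in the middle of a lobe is the protocol's own example of doubt. Those cases are decided in a meeting that includes a nuclear medicine physician, and nothing requires the pathologist to have committed to a location first. If doubt tends to be resolved towards the scan, the index test helps to define its own reference standard. At stake are sensitivity, NPV, the false-negative count that drives the end-of-study safety rule in 8.4.1 and, to a small extent, the primary endpoint.

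**Working it through.** **1. What is and is not blinded.** Central pathologists are blinded to allocation (8.2.2). The PET result is withheld from patients and treating physicians (8.3.1); pathologists are not named there. No section orders the steps so that the histological location is recorded before PET is known.

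**2. Inputs.** Pooled planning data (1.3 and Appendix IV): 55 true positives, 87 false positives, 80 true negatives and 3 false negatives, 225 in total, of whom 83 are PET-negative. Arms of 88 and 44 (4.4). Planned difference 73.1% − 40.3% = 32.8 points (4.4).

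**3. Expected false negatives with a specimen.** By plan, PET-negative nodules are operated on only in arm B: 44 × 3/225 = 0.59.

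**4. Effect of one false negative relabelled as true negative.**
- Sensitivity, arm B alone: expected true positives 44 × 55/225 = 10.8. With one false negative, 10.8/11.8 = 91.5%; without it, 100%. Change: 8.5 points.
- Sensitivity, pooling true positives of both arms: 132 × 55/225 = 32.3. With one false negative, 32.3/33.3 = 97.0%; without it, 100%. Change: 3.0 points.
- NPV, arm B: expected PET-negatives 44 × 83/225 = 16.2. With one false negative, 15.2/16.2 = 93.8%; without it, 100%. Change: 6.2 points.

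**5. Safety rules.** The stated boundaries reproduce. With p = 0.05 and one-sided α = 0.025, P(X ≥ 4 of 22) = 0.0222 (0.0948 for 3 or more), and P(X ≥ 6 of 44) = 0.0216 (0.0675 for 5 or more). The protocol gives no rate of doubtful cases, so assume that 0%, 10% or 20% of false negatives are relabelled. The chance of reaching each boundary is then:

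| True false-negative probability | Boundary | 0% | 10% | 20% |
|---|---|---|---|---|
| 10% | 6/44 | 0.274 | 0.201 | 0.137 |
| 15% | 6/44 | 0.664 | 0.556 | 0.436 |
| 10% | 4/22 | 0.172 | 0.130 | 0.094 |
| 15% | 4/22 | 0.425 | 0.345 | 0.267 |

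This shows how sensitive the rules are; it does not show that relabelling happens. The interim analysis took place in April 2018 (9.5 addendum), so only the 6/44 rule still lies ahead.

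**6. Primary comparison.** PET-positive nodules are operated on in both arms, and randomisation makes their expected share equal (142/225 = 63%). Drift towards PET among them shifts both arms alike and largely cancels. What remains is PET-negative cancer in arm B. If every such case were doubtful and relabelled, the arm B rate would rise by 0.59/44 = 1.3 points. The primary analysis concerns nodules over 10 mm. If all three planning false negatives were in that group of 186, the figure would be 3/186 = 1.6 points. One actual case is worth 1/44 = 2.3 or 1/30 = 3.3 points, which is the value of a whole case and not an expected bias.

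**7. Allocation.** The multifocality rule in 8.3.4 notes that an FDG-negative nodule is operated on in the control arm only. Apart from the crossovers foreseen in 8.5 and 10.1, a pathologist shown a negative PET for a resected nodule knows the patient was in arm B. That defeats the blinding promised in 8.2.2.

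**The case against.** The strongest reply is that the consensus settles anatomy and not diagnosis. It sits under the lesion-by-lesion qualification of the PET result, while tissue diagnosis belongs to the pathologist panel. A reader might infer that histology itself is labelled with PET in view; the text does not say that. Nor is the nuclear medicine physician's presence a flaw in itself, since someone must state where the PET focus lies.

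There are also safeguards. The index nodule is fixed by cytology and ultrasound before the scan, and scans are not reported locally. Section 8.3.4 describes histology review before tissue is related to PET. The multifocality rule works against PET, because a PET-positive contralateral cancer does not rescue a negative index nodule.

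A reader might also infer a material bias in the primary result, because every nodule operated on by plan in arm A is PET-positive while about 37% of those in arm B are not. That overlooks the 63% of arm B that are PET-positive, where any drift offsets arm A. Likewise, 132 × 3/225 = 1.8 false negatives is the wrong base: it includes arm A patients whose surgery is cancelled and who have no specimen to match.

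All of this limits the point but does not remove it. The described order of work is not a blinding rule, and location remains part of the malignancy definition.

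**Conclusion.** The gap is real and narrow. The protocol does not keep the location component of the reference label independent of PET, and the cases exposed are those it names as doubtful. Their number is not given and is probably small. Bias towards PET is a risk, not an established fact.

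The risk bears mainly on the true/false classification, sensitivity, NPV and the control-arm false-negative count, where about 0.6 expected events among 44 make one case influential. The primary comparison is barely touched: about 1.3 points on planning figures (up to 1.6 for nodules over 10 mm), even if every PET-negative arm B cancer were doubtful and relabelled. These sizes rest on the planning rate of 3/225 and on surgery following the protocol. The loss of allocation blinding for operated PET-negative nodules needs no such rate; it follows from the design. Because the remedy is cheap, it should be made.

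**What to change.** In 8.2.2, extend the blinding of central pathologists to the PET result.

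In 8.3.4, set the order of work:
1. The pathologist, with the surgeon where needed, records and locks the histological diagnosis and whether the malignancy lies in the index nodule. They use the specimen and the ultrasound position and size, without the PET result.
2. The nuclear medicine physician records and locks PET location and positivity without histology.
3. Only then are the two matched. A consensus that includes the nuclear medicine physician may settle remaining PET-to-specimen matching, but may not change the locked benign/malignant label of the index nodule.

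Report the number of consensus cases, and repeat the accuracy estimates, the false-negative count and the primary comparison with those cases classified the other way.

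The cost is wording and a small change in the order of work. Central histology review is planned for after all surgery and involves the same people, so no extra patients, visits or specimens are needed.

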8.3.5 Tissue genetic analysis

All cytology specimens will be genetically profiled using various molecular biomarkers. These tissue markers will include point mutations (e.g. BRAF and RAS point mutations), gene fusions and gene rearrangements (e.g. RET/PTC and PAX8/PPARγ rearrangements), gene and miRNA expression profiling, and copy-number variations, and possibly immunocyto- and immunohistochemical markers.

Testing techniques for molecular tissue biomarkers are rapidly developing globally. Nonetheless, as mentioned in a previous paragraph, these techniques are not yet available at Radboudumc (§1.10 Laboratory infrastructure and available techniques).

We will perform molecular diagnostics at the Leiden University Medical Centre (LUMC) (at the pathology lab of prof. dr. [name]) using state of the art next generation sequencing techniques and biomarker panels. For this purpose, cytology slides from all study participants will be sent to the LUMC. Informed consent was obtained from the study participants for these analyses.

Molecular testing on cytology requires the extraction of ± 20 ng of DNA/RNA from the existing cytology slides. To extract sufficient nucleotides, part of the cytological material will be scraped of one or two cytology slides from each patient. Prior to DNA/RNA extraction, all cytology slides

will be scanned and digitally stored; these images will be made available to and saved at the hospital where the FNA was performed, in order to enable any desired morphological review of cytology in the future. This method is also regularly used in a clinical setting. Destruction of (parts of) cytology slides disables any further staining, immunocytochemistry or other cytology testing in the future. However, as cytology review has already been completed at that point in the current study and the individual patient's treatment has been determined and executed (i.e. most patients will have undergone surgery), this will have no consequences for individual patient.

If appropriate, some cytology and histology samples may additionally be selected for further molecular testing at LUMC. This may e.g. concern Hürthle cell lesions and any copy number variations detected.

Obtained genetic profiles will be matched to the histopathological diagnosis and characteristics, to (pre-operative) clinical characteristics and to the results of the FDG-PET/CT scan, in order to evaluate underlying associations. Moreover, we would like to evaluate potential additional (molecular) tests that could enhance FDG-PET/CTs specificity (and sensitivity).

Results of the tissue genetic analysis on cytology are not used to determine patient management, but solely for investigative/explorative purposes. However, if the result of the gene expression classifier or any additional genetic testing would show a high or definitive risk of malignancy, in a patient that did not undergo diagnostic surgery (i.e. the patient was randomized to the experimental study arm with a negative FDG-PET/CT (possible false-negative) and was advised watchful-waiting instead of surgery, or the patient chose not to undergo surgery for other reasons), the patients' treating physician will be informed of the genetic results and advised to undertake appropriate action (i.e. further diagnostics or advise to undergo surgery).

8.4 Withdrawal of individual subjects

Subjects can leave the study at any time for any reason if they wish to do so without any consequences. The investigator can decide to withdraw a subject from the study for urgent medical reasons.

8.4.1 Specific criteria for withdrawal (at the end of the study)

The false-negative FDG-PET/CT ratio is expected to be around 1.3%, but we accept a falsenegative ratio of up to 5% (i.e. the a priori risk of malignancy in any thyroid nodule). After

EFFECTS

inclusion and surgery of all 44 patients in the control study-arm, final analysis will be performed. In case 6 or more of all these 44 patients (π_1 *=13.6%) in the control study-arm have a false-negative FDG-PET/CT, the treating physicians of all PET-negative patients from the experimental study arm will be advised to proceed to diagnostic (hemi)thyroidectomy. This number is based on the cumulative binomial distribution, by solving:

$$\sum_{n=X}^{n=N} \binom{N}{X} \cdot p^X \cdot (1-p)^{N-X} \le \alpha$$

With N=44, p=0.05 and α =0.025 (Bonferroni-adjusted), resulting in X≥6. Single-sided testing was used. Figure 7, p57.

[figure not shown]

Figure 7: Cumulative Binomial Distribution for a sample size of 22 (interim-analysis) or 44 (end-of-study evaluation) for an individual patient probability of a false-negative FDG-PET/CT of 0.05. In case that more than 4/22 patients (18.2%) at time of the interim analysis or 6/44 (13.6%) patients at time of the end-of-study evaluation have a false-positive FDG-PET/CT (in the control study arm), the false-negative probability is larger than the maximum accepted value of 0.05.

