1.5 Concerns and shortcomings

Recently, Deandreis et al. [20] described 55 patients scheduled for surgery of FNACindeterminate thyroid nodules. Of the nodules, 61% was benign and 18% definitely malignant. The remaining 21% was of uncertain malignant potential. They described a positive and negative predictive value of 57% and 81% respectively for definite and uncertain malignant TNs. They reported 5 FDG-PET/CT false negative lesions (3 tumours of uncertain malignant potential, 2 papillary carcinomas of 10 and 20mm) and they explain the discordance of their findings compared to other publications, by suggesting that it may be related to the definition of "indeterminate cytology" itself or to the heterogeneity of the pathology itself (small and/or well-differentiated tumours show limited FDG-uptake). There is an exceptionally large fraction of lesions with uncertain malignant potential and it can be debated whether these lesions should have been qualified as benign or malignant. The authors chose the latter, but a negative predictive value of 92% can be computed when these lesions of uncertain malignant potential are considered benign, which is much more concordant with previous reports in literature. Twenty-five of 55 scans (45%) were FDG-PET/CT negative, comparable to our meta-analysis (37%).

False-positivity, or a poor positive predictive value, may also be a concern, as these patients still undergo unbeneficial surgery. The only independent predictive factor for FDG-uptake was cellular atypia (present in both benign and malignant nodules). Current literature mainly focuses on FDG-uptake in known thyroid carcinoma [21-24] or (in vitro) in thyroid cells [25], therefore the limited specificity of FDG-PET/CT for (FNAC-indeterminate) thyroid nodules is still poorly understood. Whether previously described diagnostic tests (e.g. immunohistochemistry, gene expression classification) show complementary or additional value needs to be determined.

To our knowledge no studies have been performed to investigate the effect of a wait-and-see policy in patients with a very low probability of malignancy in cytological indeterminate nodules. The effects on HRQoL and costs are only modelled and not prospectively evaluated.

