8.7 Premature termination of the study (interim-analysis)

The false-negative FDG-PET/CT ratio is expected to be around 1.3%, but we accept a falsenegative ratio of up to 5% (i.e. the a priori risk of malignancy in any thyroid nodule). After inclusion and surgery of 22 (50%) patients in the control study-arm, an interim analysis will be performed by the safety committee (§9.5: Data Safety Monitoring Board (DSMB) / Safety Committee, p62). In case 4 or more of these first 22 patients (π_1 *=18.2%) in the control studyarm have a false-negative FDG-PET/CT, the study will be terminated preliminarily and the physicians of all PET-negative patients in the experimental study arm will be informed to advise them to undergo diagnostic (hemi)thyroidectomy. This number is based on the cumulative binomial distribution, by solving:

$$\sum_{n=X}^{n=N} \binom{N}{X} \cdot p^X \cdot (1-p)^{N-X} \leq \alpha$$

With N=22, p=0.05 and α =0.025 (Bonferroni-adjusted), resulting in X≥4. Single-sided testing was used. Figure 7, p57.

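### The false-negative safety rule tests against a 5% limit justified by malignancy, but section 8.3.4 also counts PET-negative NIFTP, FT-UMP and WDT-UMP, so the counted event and the limit need one definition

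*Protocol*

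**What the plan says.** **The rule.** Section 8.4.1 sets the end-of-study trigger, "In case 6 or more of all these 44 patients", from a one-sided binomial calculation with N=44, p=0.05 and α=0.025, "resulting in X≥6". Section 8.7 sets the interim trigger in the same way with N=22, "resulting in X≥4": if that many control patients "have a false-negative FDG-PET/CT, the study will be terminated preliminarily". Both sections lead to surgery being advised for PET-negative patients in the experimental arm.

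**The limit and the expectation.** Both sections expect a ratio of about 1.3% and explain the null rate as a malignancy risk: "we accept a falsenegative ratio of up to 5% (i.e. the a priori risk of malignancy in any thyroid nodule". Section 4.4 gives 1.3% as 3/225. Section 1.3 and Appendix IV show that the 3 are malignancies found at surgery after a negative scan.

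**The counted event.** Section 8.3.4 says of NIFTP, FT-UMP and WDT-UMP: "These are strictly considered benign though potentially precancerous lesions, for which thyroid lobectomy is justified". It then makes a scan true-positive if an avid nodule holds any histology that warrants surgery, these three included, and adds: "If such a nodule is non-FDG-avid, it will be considered false-negative". Section 10.3 sends the reader to section 8.3 for the true/false definitions.

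**Other text on the same event.** SO1c, the multifocality paragraph of section 8.3.4 and section 13.1.2 (item j) speak of malignancy only.

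**The concern.** The rule's numerator and its null rate appear to describe different events. Both 5% and 1.3% are justified as malignancy rates, whereas the definition in section 8.3.4 takes in lesions that the same section classes as benign. Neither 8.4.1 nor 8.7 limits the count to malignancy, and neither re-derives the limit, the expectation or the cut-offs for the wider event.

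The protocol knows that this choice matters. Section 1.5 discusses a series of 55 patients: "They reported 5 FDG-PET/CT false negative lesions (3 tumours of uncertain malignant potential, 2 papillary carcinomas of 10 and 20mm". It argues that the lesions of uncertain potential can be regarded as benign, which raises that series' negative predictive value from 81% to 92%. Section 8.3.4 takes the opposite convention.

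At stake is the end-of-study safety conclusion. Suppose 6 of 44 control patients had a PET-negative relevant nodule, 2 malignant and 4 borderline. Section 8.3.4 gives 6 events and a trigger. A malignancy-only count gives 2/44 = 4.5% and no trigger. The same data would support opposite statements about whether the 5% limit had been exceeded, depending on the section followed.

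**Working it through.** **Inputs.** N=22 and 44, p₀=0.05, one-sided α=0.025 per look (8.7, 8.4.1); expected rate 3/225=1.33% (4.4); one cited series with 2 malignant and 3 uncertain-potential false negatives among 55 patients (1.5). Let q be the share of control patients with a PET-negative NIFTP, FT-UMP or WDT-UMP nodule. The protocol gives no q for this population, so I vary it from 0 to 5.5 points (3/55=5.5%), one lesion per patient.

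**Formula.** P(X≥r | n, p) = Σₖ₌ᵣⁿ C(n,k) pᵏ(1−p)ⁿ⁻ᵏ. For a trigger at either look, the sum runs over two independent blocks of 22, with x≥4 in the first block or x+y≥6 in total.

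**Step 1: reproduce the cut-offs at p=0.05.**
- Interim: P(X≥3|22)=0.0948 and P(X≥4|22)=0.0222, so 4 is the smallest count at or below 0.025.
- Final: P(X≥5|44)=0.0675 and P(X≥6|44)=0.0216, so 6 is the smallest.
- Either look: 0.0354.

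The cut-offs are correct for an event with probability 5%.

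**Step 2: missed malignancy exactly at the 5% limit, borderline lesions added (p=0.05+q).**

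| q (points) | interim | final | either look |
|---|---|---|---|
| 0 | 0.0222 | 0.0216 | 0.0354 |
| 0.5 | 0.0302 | 0.0325 | 0.0498 |
| 1 | 0.0398 | 0.0465 | 0.0675 |
| 2 | 0.0638 | 0.0847 | 0.1129 |
| 3 | 0.0941 | 0.1366 | 0.1710 |

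Solving for a tail of exactly 0.025 gives p=5.19% at the interim and 5.17% at the end. So q of 0.19 or 0.17 points, about 0.2, is enough.

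**Step 3: missed malignancy at the expected 1.33% (p=3/225+q).**

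| q (points) | interim | final | either look |
|---|---|---|---|
| 0 | 0.0002 | 0.0000 | 0.0002 |
| 3 | 0.0138 | 0.0114 | 0.0208 |
| 4 | 0.0274 | 0.0285 | 0.0446 |
| 3/55 | 0.0581 | 0.0755 | 0.1022 |

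Passing 0.025 needs 5.17−1.33≈3.8 points at the final look and 5.19−1.33≈3.9 at the interim.

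**Step 4: the cited series on its own.** Malignancy only, 2/55=3.6%: 0.0076 interim, 0.0050 final. Both kinds of lesion, 5/55=9.1%: 0.1339 interim, 0.2071 final.

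**Relative size at the final look.** With 3/55 as the upper illustration, 0.0755/0.025=3.0 and 0.2071/0.025=8.3.

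**The case against.** **The null may already be the wider event.** The Figure 7 caption describes 0.05 as the individual probability of a false-negative scan, and the malignancy risk appears only in a parenthesis that explains the figure. A reader might infer from the mismatch that the stated 0.025 simply does not hold. The documents do not go that far: if 5% is a limit on the wider event, the error is 0.022 per look, as designed. What then fails is the justification, because both 5% and 1.3% are explained through malignancy.

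**The cited series is a poor guide to size.** Section 1.5 itself says that its fraction of uncertain-potential lesions is exceptionally large. This stands, so 3/55 is an upper illustration and not an estimate for this trial. A reader might also set the either-look 0.246 for 5/55 against 0.025 and speak of a tenfold error. That compares a two-look probability with a per-look level; the final-look ratio is at most 8.3 in these illustrations.

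**NIFTP may already be in the older counts.** The title of reference 65 shows that NIFTP renames a lesion formerly labelled carcinoma, and the 1.3% comes from a 2011 meta-analysis. For NIFTP, section 8.3.4 may therefore preserve the older event. The protocol does not say, so it cannot be assumed that NIFTP adds to the count.

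**Counting precursors is cautious.** Section 8.3.4 calls lobectomy justified for these lesions, and the bias is towards triggering too often, not towards missing excess malignancy. This is a fair argument for a wider rule, but such a rule needs its own limit and expectation.

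**The interim has passed.** The addendum to section 9.5 records that the April 2018 interim led to continuation without changes, so a reader should not infer that early termination is still at risk. The end-of-study evaluation in 8.4.1 remains.

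**Conclusion.** The protocol uses two definitions of a false-negative scan, and the safety rule draws its count from one and its limit from the other. Read as the protocol justifies the limit, the 0.025 per-look error fails with about 0.2 points of PET-negative borderline lesions on top of a 5% missed-malignancy rate. At the expected 1.3% it would take about 3.8 points. Read as a limit on the wider event, the error holds but the figures have no stated basis. One of the two must be corrected.

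The size in this trial cannot be fixed from the documents, because the share of such lesions is not given. The calculations assume one relevant nodule per patient and evaluable histology in all 44 controls. The arithmetic of the cut-offs is not at fault, and this point does not say which event should trigger surgery advice; that choice is the sponsor's. It should be settled before the end-of-study safety evaluation.

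**What to change.** Reconcile sections 8.3.4, 8.4.1 and 8.7, together with SO1c and section 13.1.2, so that the counted event, the 5% limit, the 1.3% expectation and the stated error all rest on one definition chosen by the sponsor. If the wider event is kept, re-derive and justify the limit, the expectation and the error for it, and say whether NIFTP is already contained in the older malignancy counts.

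In the end-of-study safety report, give two counts for the control arm: malignancy only, and malignancy plus NIFTP, FT-UMP and WDT-UMP. State which one was used at the 2018 interim.

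The cost is a short amendment and one more line in the report. No new data are needed, since section 8.3.4 already provides for these entities to be distinguished at histology.
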